a. Recruitment Methods:

- i. Describe when, where, and how potential subjects will be recruited (*Describe the source of subjects. Describe the methods that will be used to identify potential subjects. Describe materials, such as advertisements, that will be used to recruit subjects (include these with submission materials. If study is a chart review, describe which records will be accessed to collect data and how you will access them* : Participants will be recruited from the telemetry inpatient service and the cardiology clinic at the Einstein Medical Center Philadelphia. Participants on the telemetry inpatient service who are started on rivaroxaban or apixaban will be identified by [name] (co-investigator), a staff pharmacist who verifies new medication orders for telemetry inpatients, while participants in the cardiology clinic will be identified by the patient's cardiologist who initiates the anticoagulant in the clinic. The division of cardiology at Einstein Medical Center supports this study and all cardiologists will be informed about the study. Identified patients will be given a written description about the study and [name] (principal investigator) will be notified. All identified patients will have their medical records/chart reviewed by [name] to determine eligibility for the study. If appropriate, he will then contact them by phone and arrange a meeting to discuss the study protocol, answer any questions and complete the consent process
- ii. Will payments to subjects be provided?
 Yes, amount and timing: 4 payments of \$10 cash each at the point of each blood draw, totalling \$40 cash
 No
 N/A

b. Inclusion and Exclusion Criteria:

- i. Describe how you will screen for eligibility (e.g. review charts, perform specific screening tests, etc.): Participants will be recruited from the telemetry inpatient service and the cardiology clinic at the Einstein Medical Center Philadelphia. Participants on the telemetry inpatient service who are started on rivaroxaban or apixaban will be identified by [name] (co-investigator), a staff pharmacist who verifies new medication orders for telemetry inpatients.

Participants in the cardiology clinic will be identified by the patient's cardiologist who initiates the anticoagulant in the clinic. The division of cardiology at Einstein Medical Center supports this study and all cardiologists will be informed about the study.

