Screening will be also be carried out by a query on the electronic medical record with a confidential report generated weekly by the Einstein's AECIS which will contain all rivaroxaban and apixaban prescriptions ordered by electronic scripts. Investigators and co-investigators will review the medical records of patients on the list to determine if they meet the inclusion criteria for the study.

Identified patients will be given a written description about the study and [name] (principal investigator) will be notified. All identified patients will have their medical records/chart reviewed by [name] to determine eligibility for the study. If appropriate, he will then contact them by phone and arrange a meeting to discuss the study protocol, answer any questions and complete the consent process

- ii. Describe the criteria that define who will be included or excluded in your final study sample:

Inclusion Criteria

- Age \geq 60 years
- GFR \leq 90 ml/L based on creatinine clearance
- Participant has been initiated on long term anticoagulation with rivaroxaban or apixaban for atrial fibrillation within four weeks of recruitment
- Participant is willing to comply with all aspects of the protocol, including adherence to medical therapy and follow-up visit
- Participant is willing to give written informed consent

Exclusion Criteria

- History of blood dyscrasias or active bleeding,
- History of hematuria
- Patients on dialysis

c. Study Timelines:

- i. Duration of an individual subject's participation in the study: 6 months
- ii. Time period anticipated to enroll all study subjects or to complete chart review: 4 months
- iii. Estimated overall study duration (*i.e. from initiation to completion of primary analyses*): 12 months

d. Study Endpoints:

- i. Describe the primary and secondary study endpoints (*i.e. the outcome(s) that the study is designed to evaluate*):

Primary endpoint - Incidence of ARN is the primary outcome of this study and this is based on a documentation of AKI (defined as an increase in baseline serum creatinine \geq 0.3 mg/dL), in the absence of any other obvious etiology for the AKI identified after a standard clinical evaluation and work up by the patient's primary care physician, cardiologist or nephrologist. This incidence will be expressed as a percentage.

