Secondary endpoint - Urinalysis measurements (particularly hematuria and proteinuria) will be analyzed for correlation with the incidence of ARN. Demographic variables including age and race will be analyzed in contingency tables using Fisher's exact test to ascertain if they are significant for the primary outcome.

- ii. Describe any primary or secondary safety endpoints (*e.g. any disease or symptom that would result in the withdrawal of that subject from the study*): Subjects will be censored from the study if anticoagulation is withdrawn for any clinical reason

e. Human Research Methods:

- i. Describe and explain the study design (*e.g. randomized, double-blind, placebo-controlled clinical trial or retrospective chart review*):

This is a prospective observational study designed to determine the incidence of ARN in 40 adult patients recently initiated on rivaroxaban or apixaban at Einstein Medical Center Philadelphia.

- ii. Describe all research activities involved in this protocol, including a study visit timeline if appropriate:

Baseline demographic data, past medical history, current medication list and baseline laboratory records (taken within the last three months) will be obtained from the patient's hospital chart and the electronic medical record. Serum creatinine and urinalysis measurements will then be repeated at monthly intervals for the first three months and then at the six-month mark. These laboratory tests will be drawn at Einstein's Klein building Suite 100 by a trained phlebotomist.

If AKI, defined as an increase in baseline serum creatinine ≥ 0.3 mg/dL from baseline, is noted in any study participant, the patient and his primary care physician or cardiologist will be notified both verbally and through a detailed letter. A standard clinical evaluation and work up will then be performed by the patient's primary care physician or cardiologist as part of the patient's usual care with referral to a nephrologist if necessary. The research team will then be notified of the result of this work up.

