- i. Describe steps that will be taken to secure the data (e.g. training, authorization of access, password protection, encryption, physical controls, certificates of confidentiality and separation of identifiers and data) during storage, use and transmission: As stated above, a study participant list containing identifiable data will be password protected and stored on the Einstein system. This list will only be able to be accessed by members of the research team. All other data will be stored in a separate database with unique but unidentifiable identification numbers. At the termination of the study the initial study participant list will be deleted.
- ii. Describe the data analysis plan, including any statistical procedures and method for determining the sample size for the study:

Incidence of ARN is the primary outcome of this study and this is based on a documentation of AKI (defined as an increase in baseline serum creatinine ≥ 0.3 mg/dL), in the absence of any other obvious etiology for the AKI identified after a standard clinical evaluation and work up by the patient's primary care physician, cardiologist or nephrologist. This incidence will be expressed as a percentage.

Urinalysis measurements (particularly hematuria and proteinuria) will be analyzed for correlation with the incidence of ARN. Demographic variables including age and race will be analyzed in contingency tables using Fisher's exact test to ascertain if they are significant for the primary outcome.

There is no data at all in the literature for the incidence of ARN with rivaroxaban or apixaban and we short-listed that number (40) based on the reported incidence for warfarin (17-37%). We are selecting the patients at highest risk (elderly, CKD) for anticoagulation-related nephropathy (ARN) and we expect that the incidence we obtain will be the highest for the population we are studying.

In terms of precision, we will calculate confidence intervals of the proportional incidence using Stata (command line `cii 40 (incidence)`). If the incidence is zero, Stata calculates the 95% confidence interval based on our sample size as 0-9%. If we only find 2 cases of ARN, Stata calculates the point estimate incidence at 5% with 95% confidence interval as 0.6% - 17%, If we find 10 cases of ARN, Stata calculates the point estimate incidence as 25% with 95%

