confidence interval as 13% to 41%, etc. Our sample is elderly, CKD subjects at higher risk hence we expect a higher incidence than in the normal population, hence a negative result will suggest very low risk in the general population.

- iii. Describe where and how data will be stored locally: Data will be stored in password protected spreadsheets on the Einstein computer network.
- iv. Specify how long data will be stored locally: 6 years after publication of the study
- v. Specify who will have access to the data locally: The research team members.
- vi. Describe process that will be followed to ensure accuracy of collected data: All data will be checked twice upon entering it into the database to ensure accuracy. All calculations and statistical tests will be confirmed by both members of the team.
- vii. Will data be sent out or received: No Yes
 - a. Who is responsible for receipt or transmission of the data? N/A
 - b. How will the data be transported? N/A

h. Provisions to monitor the data for the safety of subjects (Required only when Human Research involves more than minimal risk):

- i. Describe plans to periodically evaluate the data collected regarding both harms and benefits to determine whether subjects remain safe. Include what data will be reviewed, who will review the data and when the data will be reviewed:

This research has no additional risk above and beyond that of a blood draw and urine collection. Blood draws for serum creatinine assay will be performed by a trained phlebotomist using standard techniques. Any problems encountered during blood draws will be reported to the research staff and will be reviewed by the entire research study team as soon as they occur to determine if and when the event needs to be reported to the IRB, and if the protocol and/or consent document require modification. Each safety data will be reviewed by at least 2 members of the research team and all events will be reviewed after every 10 patients are recruited.

i. Withdrawal of Subjects:

- i. Describe the anticipated circumstances under which subjects will be withdrawn from the research without their consent: Subjects will be censored from the study if anticoagulation is withdrawn for any clinical reason

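### The only incidence the protocol names is AKI attributed to the anticoagulant after usual-care work-up, so a low figure cannot be told apart from AKI ascribed to other causes; all-cause AKI should be reported beside it

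*Protocol*

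**What the plan says.** The protocol describes a single-arm observational study "designed to determine the incidence of ARN in 40 adult patients" (Study Design, e. Human Research Methods, i).

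The primary endpoint (Study Design, d. Study Endpoints, i; repeated in g. Data Management, ii) has two parts:

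- A measured part: AKI, "defined as an increase in baseline serum creatinine ≥ 0.3 mg/dL".
- A judged part: the AKI counts as ARN "in the absence of any other obvious etiology for the AKI identified after a standard clinical evaluation and work up". The endpoint text assigns this "work up by the patient's primary care physician, cardiologist or nephrologist".

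Under e. Human Research Methods, ii, the work-up takes place "as part of the patient's usual care with referral to a nephrologist if necessary". The research team's part is then stated: "The research team will then be notified of the result of this work up". Laboratory results and work-up data are entered in the study database.

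The ARN incidence is to be given as a percentage. No other incidence is named. Two conclusions are drawn from it. Section 2 hypothesises that it is lower than the reported warfarin incidence, and the Significance text of section 3 would take that as support for renal safety. The data analysis plan adds that "a negative result will suggest very low risk in the general population".

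Under i. Withdrawal of Subjects, patients whose anticoagulation is withdrawn for a clinical reason are censored, and all their data are removed.

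**The concern.** The measured part of the endpoint is the same for everyone. The judged part is made in routine care by different physicians. The protocol states no criteria for when another cause is obvious, no minimum work-up, and no rule for an AKI whose work-up is never completed. The physicians know the drug. In the clinic, patients are identified by "the patient's cardiologist who initiates the anticoagulant in the clinic", and that cardiologist may also do the work-up.

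A low ARN percentage therefore has two possible explanations: few patients had AKI, or many did and other causes were named. The single percentage cannot separate them, although the data that could are collected.

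This matters because of how the figure will be read. The Innovation text of section 3 says the retrospective studies had to rely on assumptions because further work-up was not possible. Active exclusion of other causes here is a different process from the one behind the warfarin benchmark. Part of any gap between the two figures could come from that difference alone.

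**Working it through.** **Inputs**

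- Denominator 40 (Study Design, e.i). I assume all 40 are retained.
- Warfarin range: 16% to 37% in the Background, 17% to 37% in the data analysis plan. Both are used below.
- Number of AKI cases A among the 40: not given in the protocol. I show A from 4 to 15 as an assumption.
- Number attributed to ARN: k, any whole number from 0 to A.

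**Step 1. Reproduce the protocol's intervals.** The exact (Clopper-Pearson) 95% limits for k of n are the 2.5% quantile of Beta(k, n−k+1) and the 97.5% quantile of Beta(k+1, n−k). For k = 0 the upper limit is 1 − 0.025^(1/40) = 8.8%.

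| Cases of 40 | Estimate | Recomputed 95% CI | Protocol |
|---|---|---|---|
| 0 | 0% | 0 to 8.8% | 0–9% |
| 2 | 5% | 0.6 to 16.9% | 0.6%–17% |
| 10 | 25% | 12.7 to 41.2% | 13% to 41% |

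The stated intervals are correct.

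**Step 2. Range due to attribution alone.** For fixed creatinine data the reported incidence is k/40, so it lies between 0 and A/40.

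| AKI cases A | None attributed (95% CI) | All attributed, A/40 (95% CI) |
|---|---|---|
| 4 | 0% (0 to 8.8%) | 10.0% (2.8 to 23.7%) |
| 6 | 0% (0 to 8.8%) | 15.0% (5.7 to 29.8%) |
| 7 | 0% (0 to 8.8%) | 17.5% (7.3 to 32.8%) |
| 10 | 0% (0 to 8.8%) | 25.0% (12.7 to 41.2%) |
| 15 | 0% (0 to 8.8%) | 37.5% (22.7 to 54.2%) |

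For A = 10, intermediate attribution gives 5% (0.6 to 16.9%) if 2 are attributed and 12.5% (4.2 to 26.8%) if 5 are.

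**Step 3. When the point estimate can enter the warfarin range.** The lower end corresponds to 0.16 × 40 = 6.4 or 0.17 × 40 = 6.8 cases, so 7 are needed on either figure. With 6 or fewer AKI cases, the largest possible estimate is 15%, below the range. The upper end, 0.37 × 40 = 14.8, is passed at 15 cases.

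**Step 4. Smaller AKI counts.** With only 4 AKI cases, the two extremes still read differently. None attributed gives an upper limit of 8.8%, which excludes the whole warfarin range. All attributed gives an upper limit of 23.7%, which does not.

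**Step 5. Is all-cause AKI an upper limit on ARN?** Every ARN case is an AKI case, so ARN ≤ AKI in any fixed set of patients. Under the withdrawal rule, a patient with AKI whose anticoagulant is then withdrawn leaves the database. The inequality therefore holds for retained patients with AKI detected at study visits, and not necessarily for all who were enrolled.

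**The case against.** **ARN is a diagnosis of exclusion.** The Background and Innovation text say so and give prospective work-up as a reason for the design. All-cause AKI is a different quantity, and the warfarin condition is also defined by excluding other causes. This stands, and it is why attributed ARN should remain primary. It does not make an unstandardised exclusion visible in the result.

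**An analysis plan could add an all-AKI row.** It could, and nothing in the protocol forbids it. But the protocol has its own data analysis section, which fixes the endpoint, those who do the work-up and the way a negative result will be read.

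**A reader might infer that attribution is biased downward.** The documents do not support a direction. Knowing the drug could raise or lower attribution, and the wording leaves a case as ARN unless an obvious other cause is found. No passage says how often another cause would be named. A physician investigating possible drug-related injury has to know the drug, so lack of blinding is not a correctable fault here.

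**A reader might infer that the result will swing from near zero to the warfarin range.** That requires at least 7 AKI cases and near-extreme attribution. The protocol's 10-of-40 example refers to ARN, not AKI.

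**A reader might infer that the treating physician makes the final ARN classification.** The protocol gives that physician the work-up and sends the result to the research team; it does not say who makes the final call. This leaves the judgement no better defined.

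**A reader might want the very-low-risk statement barred unless all-cause AKI is also low.** That goes too far, since AKI with a clear unrelated cause would then block a conclusion about ARN.

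**Conclusion.** The point holds in conditional form. The protocol names one incidence, it depends on dispersed usual-care judgements, and a low value would not show whether AKI was rare or was ascribed elsewhere. Neither the comparison with warfarin nor the very-low-risk reading can be assessed from that figure alone.

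The possible shift is 0 to A/40, where A is the unknown number of AKI cases: 0 to 10% for 4 cases, 0 to 25% for 10. The point estimate reaches the stated warfarin range only from 7 cases upward. These are limits under complete or absent attribution, not a forecast, and they assume that all 40 patients are retained. The primary result remains computable; its planned interpretation is what is weakened.

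**What to change.** Keep attributed ARN as the primary endpoint and add the following to the data analysis section:

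1. Report beside it the all-cause AKI incidence (creatinine rise of at least 0.3 mg/dL from baseline) with an exact 95% confidence interval.
2. List for each AKI case the alternative cause named, or that the work-up was not completed.
3. Give a sensitivity figure in which AKI with an uncompleted work-up counts as ARN.
4. Interpret the warfarin comparison and the very-low-risk statement with both incidences shown.
5. State that all-cause AKI limits ARN from above only among retained patients with AKI detected at study visits. For it to bound the whole cohort, AKI recorded before anticoagulation was withdrawn would have to be kept, which means revising the data-removal rule under Withdrawal of Subjects.

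Items 1 to 4 need no new tests, visits or patients, since creatinine and work-up data already go into the database. The cost is one extra result line, a short listing, a sensitivity figure and a few sentences. The downside is that the all-cause figure will look less favourable and includes AKI unrelated to the drug, which the listing makes visible.

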The non-vitamin K oral anticoagulants (NOACs) are a new group of drugs which have been recently approved for use as blood thinners. They have a faster onset of action compared to warfarin and unlike warfarin, they do not need frequent monitoring. Apixaban and Rivaroxaban both have a similar mechanism of action. They inhibit Factor 10 which a clotting factor. They are the most commonly prescribed NOACs at Einstein Medical Center Philadelphia. We intend to serially monitor the kidney function by measuring the serum creatinine and urinalysis of 40 high risk patients who are recently started on either apixaban or rivaroxaban over a six month period. This will enable us to discover what proportion of patients actually develop ARN after starting a NOAC.

2) Project Objectives and Hypotheses:

Determine the incidence of ARN in high risk patients on rivaroxaban or apixaban (Factor 10 inhibitors).

Hypothesis - the incidence of ARN with apixaban or rivaroxaban is less than the previously reported incidence of ARN in warfarin.

- Describe demographic and urinalysis-associated predictors of ARN in patients on rivaroxaban or apixaban (Factor 10 inhibitors)

3) Background/Significance of Research (*Provide the scientific or scholarly background and rationale for the research based on the existing literature (include references). Describe relevant prior experience and gaps in current knowledge. Describe any relevant preliminary data. Explain the significance of the research in terms of why it's important and how it will add to existing knowledge.*):

Anticoagulation-related nephropathy (ARN) is an understudied renal complication of anticoagulant therapy that is characterized by acute kidney injury (AKI) defined as an increase in baseline serum creatinine ≥ 0.3 mg/dL, without any alternate etiology, in the setting of a supra-therapeutic International Normalized Ratio (INR) greater than 3.0 [1-7]. ARN has mainly been studied in relation to warfarin, it usually occurs in the first two months of starting anticoagulant therapy and retrospective studies have estimated the prevalence to range from 16% to 37% [4-6]. The strongest risk factor for ARN is pre-existing chronic kidney disease (CKD); other risk factors include older age, diabetes mellitus and hypertension [1,4]. Patients with ARN have an accelerated progression of CKD and a retrospective study of more than 15,000 patients on warfarin showed a 65% increase in mortality in patients with ARN [4,6].

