The non-vitamin K oral anticoagulants (NOACs) are replacing warfarin in the clinical setting for long term anticoagulation because of the advantages of faster, reliable onset of action, and unlike warfarin, they do not require dose-response monitoring [8-10].

Apixaban and Rivaroxaban both have a similar mechanism of action. They inhibit Factor 10 which a clotting factor. They are the most commonly prescribed NOACs at Einstein Medical Center Philadelphia. A few animal models and case reports have shown that these NOACs (particularly dabigatran and apixaban) can lead to deterioration of kidney function, but there is limited epidemiologic data on ARN in NOACs and the incidence of ARN in NOACs is unknown [11-14]. A proposed guideline to diagnose ARN recommends that serum creatinine and urinalysis be checked monthly in the first few months of anticoagulation [1]. Clinical trials that compared warfarin to NOACs specifically studied stroke risk and bleeding outcomes and did not document the incidence of ARN because they did not make these regular creatinine and urinalysis measurements in the first few months of anticoagulation [15-20]. Our study intends to make these necessary measurements in a selected group of high risk patients started on rivaroxaban or apixaban and hence determine the incidence of ARN in this group.

This study will be the first epidemiological study using a prospective design to measure the incidence of ARN in a population receiving NOACs. Given the high morbidity and mortality associated with ARN, the findings will enhance patient safety, enabling patients and health providers to make informed decisions with their patients regarding the choice of anticoagulants. It will also establish baseline data that will serve as foundation for future studies.

SIGNIFICANCE

Anticoagulant-related nephropathy (ARN) is a relatively new and underdiagnosed complication of anticoagulant therapy with the potential to accelerate chronic kidney disease and lead to increased mortality [4,6]. Brodsky, et al, performed a retrospective study of more than 15,000 subjects and showed that the 5-year Kaplan-Meier survival rate was significantly lower in the ARN cohort compared to the patients without ARN with a 65% increased risk of mortality [4]. This dramatic increase in mortality that is attributable to an episode of ARN in a patient taking an anticoagulant is the reason why this study is very significant.

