The clinical trials that compared the NOACs to warfarin did not specifically study ARN and did not repeat creatinine and urinalysis testing in the first two to three months of therapy to establish possible ARN diagnosis [15-20]. In most of these studies, only baseline creatinine and creatinine levels 6 to 12 months later were analyzed, hence it is possible that ARN was under-diagnosed as most cases of ARN are detected in the first eight weeks of therapy. Our study aims to accurately capture ARN cases by making these measurements monthly in the first three months of starting the anticoagulant.

This study is pivotal because it will for the first time, define the incidence of ARN in patients on rivaroxaban or apixaban therapy. If we find that ARN incidence in patients started on rivaroxaban or apixaban is less than that seen with warfarin, this can help support evidence that this NOAC is safer for the kidneys compared to warfarin and this data can enable us make evidence based decisions regarding the continued use of the medication to help our patients. If on the other hand we find that the medication leads to ARN, then we will be contributing important post-marketing surveillance data that can also help us make safety decisions about the use of the medication in the future.

INNOVATION

Previous studies on ARN have utilized retrospective study designs which have many epidemiological pitfalls including the cause versus effect bias and the inability to ascertain relative risk [1]. Our study is unique because we intend to utilize a prospective epidemiological design to study this renal complication, a first in the study of ARN. This is important because ARN is a diagnosis of exclusion and hence a prospective study is able to more accurately define cases of the condition compared to the assumptions that are made in retrospective studies where further work up cannot be done in retrospect.

This will be the first epidemiological study focused on ARN in a NOAC. Even though NOACs are new, they are becoming ubiquitous and a mainstay in clinical practice and not just an alternative to warfarin. For example, the recent CHEST guidelines recommend them as first line therapy in the treatment of venous thromboembolism [8]. Hence it will be important to clearly delineate their effects on the kidneys.

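### Nothing in the protocol keeps urine findings from informing the ARN label, yet the only urinalysis analysis it states correlates those findings with that label

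*Protocol*

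**What the plan says.** Under Project Objectives and Hypotheses, the second aim is: "Describe demographic and urinalysis-associated predictors of ARN in patients on rivaroxaban or apixaban". Study Endpoints (item d of Study Design) turns this into an analysis: "Urinalysis measurements (particularly hematuria and proteinuria) will be analyzed for correlation with the incidence of ARN". The same plan is repeated in the data analysis part of Data Management (item g). No other outcome is named for the urinalysis data.

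The outcome is built in two steps.

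- **Creatinine.** Human Research Methods (item e) starts the process this way: "If AKI, defined as an increase in baseline serum creatinine ≥ 0.3 mg/dL from baseline, is noted in any study participant". The participant and the treating physician are then notified.
- **Exclusion of other causes.** "A standard clinical evaluation and work up will then be performed by the patient's primary care physician or cardiologist", with referral to nephrology if needed, and the research team is told the result. The AKI counts as ARN "in the absence of any other obvious etiology for the AKI identified after a standard clinical evaluation and work up".

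The protocol does not list what the work-up contains. It does not say that those who judge the cause are unaware of urine results.

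The Background/Significance section gives urinalysis a diagnostic role twice. It says: "A proposed guideline to diagnose ARN recommends that serum creatinine and urinalysis be checked monthly in the first few months of anticoagulation". It also faults earlier anticoagulant trials because they "did not repeat creatinine and urinalysis testing in the first two to three months of therapy to establish possible ARN diagnosis".

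**The concern.** A predictor analysis needs an outcome that is assigned independently of the predictor. Here the second step of the outcome is a clinical judgement about cause, and urine findings are natural evidence for it. A physician could take hematuria as support for ARN, or as a sign of some other urinary or glomerular cause. Proteinuria in a patient with diabetes or hypertension could be taken as pointing away from ARN. If either happens, the finding helps to form the label and is then tested against it. This is incorporation bias.

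At stake is the urinalysis half of the second objective. A positive, null or negative correlation could not be separated into kidney injury and attribution, and a reader could not correct for it afterwards because its direction is not known. The primary incidence estimate is not the subject of this point.

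**Working it through.** **1. The plan's own figures.** The only precision figures are exact 95% intervals for ARN incidence in 40 patients. Clopper-Pearson limits give 0 to 8.8% for 0 cases, 0.6 to 16.9% for 2 cases and 12.7 to 41.2% for 10 cases. These match the stated 0-9%, 0.6%-17% and 13%-41%. They are correct, and they concern the primary endpoint, so they neither support nor weaken this point.

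**2. Where urine findings could enter.**

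- AKI step: a creatinine rise of at least 0.3 mg/dL. Urine findings play no part.
- Attribution step: physician judgement in usual care, content open, no masking stated. Urine findings can enter, from the chart or from tests the physician orders.
- Analysis step: hematuria and proteinuria against the result of the attribution step.

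**3. What that could do to the correlation.** The protocol gives none of the inputs below, so all are assumptions.

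- AKI risk is 25% with and without hematuria, so there is no true association with AKI.
- Hematuria is present in 20 to 40% of 40 patients.
- ARN risk in a group = P(AKI) × P(labelled ARN given AKI, in that group).
- The test is two-sided Fisher at 5%. The protocol names this test for the demographic tables and names none for urinalysis.

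| Share of AKI labelled ARN, hematuria present / absent | ARN risk, present / absent | Risk ratio | Fisher rejects |
|---|---|---|---|
| 60% / 60% | 0.25×0.6 = 15% / 15% | 1.0 | 1.9-2.3% |
| 70% / 50% | 0.25×0.7 = 17.5% / 0.25×0.5 = 12.5% | 1.4 | 4.3-5.4% |
| 80% / 40% | 0.25×0.8 = 20% / 0.25×0.4 = 10% | 2.0 | 9.5-11.0% |
| 30% / 70% | 0.25×0.3 = 7.5% / 0.25×0.7 = 17.5% | 0.43 | 0.3-3.9% |

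With AKI risk varied from 25 to 50%, labelling at 70% / 50% gives odds ratios of about 1.5 to 1.6 and rejection in 4 to 8%. Labelling at 80% / 40% gives 2.25 to 2.67 and 10 to 22%. An extreme 90% / 30% gives 3.6 to 4.6 and 19 to 48%. Where labelling ignores urine, rejection stays at 2 to 3%.

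**4. What all-cause AKI can and cannot show.** Creatinine-defined AKI skips the attribution step, so in every row above it would show 25% against 25%. The reverse inference fails. Suppose hematuria truly marks ARN (20% against 10%) and AKI from other causes runs the other way (5% against 15%). All AKI is then 20 + 5 = 25% against 10 + 15 = 25%, the same picture from a real ARN-specific link. If other-cause AKI is 15% in both groups, all AKI is 35% against 25%. A true ARN ratio of 2.0 is diluted to 1.4, and Fisher rejects in about 7 to 8%. A gap between the two outcomes is therefore a warning and does not prove attribution.

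**The case against.** The strongest reply is that the written ARN definition has no urinalysis criterion. It uses a creatinine rise and the absence of another obvious cause. The two background statements describe a cited guideline and the gaps of earlier trials. They do not say how cases are assigned in this study. Study urinalysis is done for research, samples carry a study number, and results go to a database for the research team. The notice to the physician is triggered by AKI, and no urine result is mentioned in it. This stands. A reader might infer that urinalysis decides the label and that the predictors are built in by definition. The documents do not support that reading; they leave the route open without stating that it is used.

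Second, a history of hematuria is an exclusion, and baseline samples are less exposed to the problem. This also stands in part. However, the same exclusion should make baseline hematuria uncommon, so the hematuria analysis is likely to lean on follow-up samples, where the risk is more direct. Baseline urinalysis comes from the chart, which the treating physician can be expected to see, so earlier samples reduce the risk without removing it.

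Third, the labelling rates are invented, the direction is unknown, and with 40 patients a formal false positive is uncommon in the moderate scenarios. This is correct, and it is why no size can be claimed. It does not make a reported ratio interpretable.

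Fourth, the choice of sample and supplementary analyses often belong in an SAP. The choice of sample is therefore not raised as a fault in itself. But the protocol fixes ARN as the outcome of the urinalysis correlation twice, once in its own data analysis plan, and that choice is open to comment here.

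**Conclusion.** The point holds as an uncontrolled risk to a secondary objective. ARN is a physician-judged diagnosis of exclusion, nothing keeps urine findings out of that judgement, and the stated analysis sets urine findings against the resulting label and describes the results as predictors. An observed association, positive or negative, could partly reflect attribution.

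Its size cannot be derived from the documents. The ratios of 0.43 to 2.0 at an AKI risk of 25%, and the odds ratios up to 4.6 in the extreme case, rest wholly on assumed AKI risks and labelling rates. They show what is possible and do not forecast a result.

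A reader might also infer that an association seen with ARN but absent for all AKI must be an artefact of labelling. The 25% against 25% example shows that this does not follow. Nor does the argument reach the age and race tables, since it concerns urine findings only.

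**What to change.** In Study Endpoints and in the data analysis part of Data Management:

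- Keep ARN as the outcome for the urinalysis correlations.
- Beside each ARN result, report the same correlation against creatinine-defined AKI of any cause (a rise of at least 0.3 mg/dL). Use all analysed participants, bearing in mind that the protocol removes the data of those censored after anticoagulation is withdrawn.
- Use urinalysis taken at baseline or before the AKI for both, and say which sample serves for participants without AKI.
- State that an association seen with ARN but not with all AKI may reflect either attribution or a true ARN-specific link, and will not be reported as an established predictor.
- Leave the Fisher tables for demographics as planned.

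The cost is wording and one extra set of small tables. No new visit, sample or patient is needed, and clinical care does not change. There are two drawbacks. The all-AKI outcome is less specific to ARN. Restricting to earlier samples also leaves fewer hematuria findings to analyse.
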